## **6 INVESTIGATIONAL PRODUCT**

### **6.1 Manufacturing and Storage**

The investigational product will be provided to KGK by the Sponsor. The investigational product will be carefully stored at the study site in a lockable, limited access area, accessible only to study team personnel in compliance with pertinent regulations. Only authorized persons will have access to the investigational product. The products will be stored at room temperature and will not be exposed to direct sunlight or heat. The investigational products will be kept in a locked investigational product storage room at KGK Science Inc. on receipt. An accountability log will be kept for the investigational products.

All unused investigational product will be returned to the study sponsor by KGK (at the sponsor's expense) or destroyed on receipt of written confirmation from the sponsor at study closeout (within one month of last participant visit).

Manufactured by: Hofseth Biocare ASA  
[name]

### **6.2 Labeling and Coding**

The investigational product will be labeled according to the requirements of ICH-GCP guidelines and applicable local regulatory guidelines.

### **6.3 Investigational Product**

Dietary Ingredient	Quantity (Qty)
Salmon protein hydrolysate (ProGo®)	4000 mg

Non-medical ingredients: 750 mg Forest Fruit Flavoring (made up of Malic acid, Sucralose, Forest Fruit SY653533, Beetroot Powder, and Lecithin)

### **6.4 Directions**

Participants will be instructed to take 4.75 g powder in individual sachets (4 g Salmon Protein Hydrolysate (ProGo®) + 750 mg Forest Fruit Flavoring) mixed in 100-300 mL of water daily at breakfast for 128 days. Participants will be instructed to consume the product within 5-10 minutes of mixing with water. Clinic staff will instruct participants to save all unused and open packages and return them to KGK for a determination of compliance. If a morning dose is missed participants are instructed to take the dose as soon as possible after breakfast at any time during the same day. Participants will be advised not to exceed 2 sachets daily.

Protocol 18PEHH:	A proof-of-concept study to evaluate the efficacy of Salmon Protein Hydrolysate Powder on energy increase and anti-inflammatory modulation in healthy males and females.
------------------	--

## 7 STUDY ASSESSMENTS

See 14.1 for the schedule of assessments.

### 7.1 Visit 1; Screening (Day -45 to Day -1) \*

*\* At the discretion of the Qualified Investigator, any participants falling outside of the screening window (Day -45 to Day -1) due to scheduling issues may be asked to repeat eligibility/screening procedures prior to enrolment.*

At screening, an informed consent form will be given to the potential volunteer. They will be required to read the information and will be given the opportunity to seek more information if needed, or provided with the option of taking the consent form home to review prior to making their decision. If agreeable, the volunteer will sign the consent form and receive a duplicate of the signed copy. Once consent has been obtained, the screening visit will proceed. Each volunteer will be sequentially assigned a screening number to be entered in the screening and enrollment log. No fasting is required for this visit.

Screening assessments include:

1. Obtain informed consent
2. Review inclusion and exclusion criteria
3. Review medical history and capture recurring conditions
4. Review concomitant therapies and current health status
5. Weight and height measurements for BMI calculation (Section 7.5.2)
6. Waist and hip circumference measurements (Sections 7.5.3 and 7.5.4)
7. Seated resting blood pressure and heart rate measurements (Section 7.5.5)
8. Urine pregnancy test for female participants of child bearing potential
9. Physical Examination (excludes genital and rectal examination)
10. Collect blood sample for CBC
11. Administer Product Tolerance Questionnaire to assess participants' response to product (see 14.2)

The next visit will be scheduled for potentially eligible participants in  $\leq 45$  days.

Reminders for participants prior to their next in-clinic visit:

1. Refrain from consumption of supplements as per Section 5.3.2.
2. Maintain current dietary and exercise habits
3. 8-hour fast prior to next visit

### 7.2 Visit 2; Baseline (Day 0)

Eligible participants will return to the clinic for baseline assessments. An 8-hour fasting period is required for this visit.

Baseline (Day 0) assessments include:

1. Review inclusion and exclusion criteria
2. Review concomitant therapies and current health status and identify pre-emergent adverse events

Protocol 18PEHH: A proof-of-concept study to evaluate the efficacy of Salmon Protein Hydrolysate Powder on energy increase and anti-inflammatory modulation in healthy males and females.

3. Weight measurement (BMI calculation)
4. Waist and hip circumference measurements
5. Seated resting blood pressure and heart rate measurements
6. Urine pregnancy test for female participants of child bearing potential
7. Two buccal cell swabs will be collected for DNA analysis (Section 7.5.6)
8. Collect blood samples for future analysis (Section 7.5.8):
  - o Oxidative stress-related gene expression (Sections 7.5.8.1 and 14.5)
  - o Total ROS/RNS free radical activity (Section 7.5.8.2)
  - o Human inflammatory cytokine levels (Section 7.5.8.3)
9. Collect blood samples for HbA1c and fasting glucose
10. Complete Vitality and Quality of Life Questionnaire (Section 14.2)
11. Complete Hair, Nails, and Skin Self-Assessment Questionnaire (Section 14.4)
12. Dispense investigational product and instruct participants on use
13. Dispense study diary instructions for participants (record daily product use, changes in concomitant therapies, and any adverse events throughout the study).

The next visit will be scheduled for Week 18 (Day 128 ± 3).

Reminders for participants prior to their next in-clinic visit:

1. Follow instructions on consumption of the investigational product and log any irregularities or missed doses in the subject diary
2. Refrain from consumption of supplements as per Section 5.3.2.
3. Complete and bring subject diaries on the next visit if diary is not completed using the app
4. Maintain current dietary and exercise habits.
5. Bring unused investigational product in the original packaging to next visit.
6. 8-hour fast prior to next visit

### 7.3 Compliance Phone Calls

Participants will be contacted via telephone at Week 6 and Week 12 to ensure compliance to study product and study processes.

### 7.4 Visit 3; End-of-Study; Week 18 (Day 128 ± 3)

Participants will return to the clinic for Visit 3 assessments with any unused investigational product and completed study diaries if any. An 8-hour fasting period is required for this visit.

Visit 3 assessments include:

1. Return unused investigational product in the original packaging and remnants and calculation of compliance by counting the returned unused investigational product
2. Ensure that study apps have been reviewed
3. Collect and review study diaries if applicable
4. Weight measurement (BMI calculation)
5. Waist and hip circumference measurements

Protocol 18PEHH: A proof-of-concept study to evaluate the efficacy of Salmon Protein Hydrolysate Powder on energy increase and anti-inflammatory modulation in healthy males and females.

6. Seated resting blood pressure and heart rate measurements
7. Collect blood sample for CBC
8. Collect blood samples for future analysis (Section 7.5.8):
  - Oxidative stress-related gene expression (Sections 7.5.8.1 and 14.5)
  - Total ROS/RNS free radical activity (Section 7.5.8.2)
  - Human inflammatory cytokine levels (Section 7.5.8.3)
9. Collect blood samples for HbA1c and fasting glucose
10. Complete Vitality and Quality of Life Questionnaire (Section 14.2)
11. Complete Hair, Nails, and Skin Self-Assessment Questionnaire (Section 14.4)
12. Physical Examination (excludes genital and rectal examination)
13. Review concomitant therapies and adverse events

## **7.5 Clinical Assessments and Procedures**

Calculations or measurements of specific parameters are required as indicated in the schedule of assessments. Instructions for determining these parameters are provided in the following sections.

### **7.5.1 Questionnaires**

Product Tolerance Questionnaire will be completed at Visit 1 for screening (see Section 14.2).

Vitality and Quality of Life Questionnaire for energy levels will be completed at Visit 2 and Visit 3 (see Section 14.3)

Hair, Nails, and Skin Self-Assessment Questionnaire will be completed at Visit 2 and Visit 3 (see Section 14.4)

### **7.5.2 Height, Weight**

Weight measurements will be performed with shoes removed, and bladder empty. Participants will be weighed on the same scale at all visits.

At least two separate measurements will be taken at each visit. If the two measurements are more than 0.5 kg (1.1 lbs.) apart, a third measurement will be taken. Then the two closest values will be selected and entered in the database.

Measurement of height will be performed with the participant's shoes removed. The participant's knees will be straightened, and head held upright.

### **7.5.3 Waist Circumference**

The waist circumference is measured at the part of the trunk located midway between the lower costal margin (bottom of lower rib) and the iliac crest (top of pelvic bone) while the participant is standing. The measurer should stand beside the participant and fit the tape tightly against the skin but without compressing any underlying soft tissues. The circumference should be measured at the end of a normal expiration. At least two separate measurements should be taken at each visit. If the two measurements differ by more than 10%, a third measurement should be taken. Then the two closest values will be selected and entered into

Protocol 18PEHH:

A proof-of-concept study to evaluate the efficacy of Salmon Protein Hydrolysate Powder on energy increase and anti-inflammatory modulation in healthy males and females.

the database. The method of measurement for waist circumference is from the Waist Circumference and Waist-Hip Ratio report of a WHO Expert Consultation, Geneva 8-11 December 2008.

#### **7.5.4 Hip Circumference**

While participant is standing upright, place a measuring tape around the greater trochanteric prominence (the widest part of the hips). Hold tape firmly but do not press the tape into the skin. Make sure the tape is parallel to the floor. Record the reading. At least two separate measurements should be taken at each visit. If the two measurements differ by more than 10% a third measurement should be taken. Then the two closest values will be selected and entered into the database. The method of measurement for hip circumference is from the Waist Circumference and Waist-Hip Ratio report of a WHO Expert Consultation, Geneva 8-11 December 2008.

#### **7.5.5 Blood Pressure**

In office, seated resting blood pressure and heart rate will be determined from 3 measurements obtained at least 1 minute apart. One arm will be chosen and used consistently throughout the study. Blood pressure will be checked in both arms at the first examination. If a consistent inter-arm difference exists, the arm with the higher pressure will be used throughout the study. The arm selected for use at the initial visit will be documented in the study file.

The participant should be seated comfortably with the back supported and the upper arm bared without restrictive clothing. Feet should be flat on the floor, legs will not be crossed. The participant will rest in this position for at least 5 minutes prior to the first reading.

As per the QI a high office blood pressure should be rechecked after participant is given a glass of water and is seated for 15 min. Also, participant should be queried about their usual blood pressure.

The same recording method and the same equipment will be used for each participant throughout the study.

#### **7.5.6 Buccal Cell Swab Collection**

Buccal cell swabs will be collected at baseline (visit 2) at the KGK Science clinic site to analyze single-nucleotide polymorphisms (SNPs) to identify responders vs. non-responders. The clinic coordinator will verify that the participant's mouth is empty and that the participant is still fasting. The clinic coordinator will sanitize their hands and don a mask and gloves. A sterile brush will be carefully removed from the collection package. Caution is exercised not to touch the swab tip with gloves or against any surface. The participant will be asked to open his or her mouth and the inside of the mouth will be scraped 10 times using the Buccal Collection brush against the inside of the cheek. The brush will be removed immediately without touching the brush against teeth, lips or other surfaces. The collection brush will then be removed from its handle using sterile scissors or a razor blade and placed into a microcentrifuge tube containing 300  $\mu$ L of cell lysis solution. This process will then be repeated using a fresh brush to generate a second buccal swab sample. The samples will be sent to Stanford for DNA analysis.

#### **7.5.7 Sample Preparation for RNA**

One EDTA blood tube will be used for stabilization of whole blood RNA. The whole blood will be aliquoted into 6 cryovials- each containing 500  $\mu$ L of whole blood. 1.3 mL of *RNAlater* will then be added to each cryovial to stabilize the whole blood RNA. The tubes will then be gently mixed 5 times and the samples will be stored at -40°C for future analysis (see Section 7.5.8.1).

Protocol 18PEHH:

A proof-of-concept study to evaluate the efficacy of Salmon Protein Hydrolysate Powder on energy increase and anti-inflammatory modulation in healthy males and females.

## 7.5.8 Future Analyses

### 7.5.8.1 *Oxidative Stress-Related Gene Expression*

Previous *in vitro* experiments using PCR gene-array to evaluate the efficacy of SPH on oxidative stress, showed up- and down-regulation of multiple human oxidative stress-related genes. The present study will evaluate the same effects of the investigational product *in vivo* (Section 14.5).

The PCR array is a highly sensitive and reliable method for the analysis of multiple genes. It will be used to analyze expression levels of 84 genes related to oxidative stress by determining which, if any, oxidative stress genes will be impacted by supplementation with the investigational product.

RNA samples will be prepared for this analysis (Section 7.5.7) and stored at -80 C.

### 7.5.8.2 *Total ROS/RNS free radical activity*

Measuring the effect of antioxidant interventions and ROS/RNS activity is crucial to suppressing or managing oxidative stress reducers. Previous studies have shown that fish protein hydrolysate has antioxidant properties (Girgih et al., 2013).

An ROS/RNS Assay kit will be used for measuring total ROS/RNS free radical activity to evaluate the efficacy of the investigational product on the presence of free radicals. The kit will measure the total free radical presence of a sample using green fluorescence techniques. Fluorescence intensity is proportional to the total ROS/RNS levels within the sample. Free radical molecules are representative of both ROS, and RNS, which allows for the measurement of total free radical population within a sample.

Serum samples will be centrifuged at 10,000 x g for 5 minutes and stored at -80°C.

### 7.5.8.3 *Human Inflammatory Cytokine Levels*

In a previous study, supplementation with the investigational product showed significantly lower IL-6 levels in comparison to a control (Framroze et al., 2016). The current study will evaluate the efficacy of the investigational product on levels of inflammatory cytokines, which includes IL-1RA, IL-4, IL-6, IL-10, IL-11, IL-13 and TGF-β.

Inflammatory cytokine levels will be measured using a multi-analyte ELISArray kit. This kit enables the analysis of protein expression for multiple protein targets.

Serum samples will be centrifuged for 15 minutes at 1000 x g within 30 minutes of collection and then stored at  $\leq -20^{\circ}\text{C}$ .

## 7.5.9 Compliance

Compliance will be assessed by counting the returned unused study product at each visit. Compliance is calculated by determining the number of dosage units taken divided by the number of dosage units expected to have been taken multiplied by 100.

$$\frac{\text{number of dosage units taken}}{\text{number of dosage units expected to have been taken}} \times 100\%$$

In the event of a discrepancy between the information in the treatment diary and the amount of study product returned, use will be based on the product returned unless an explanation for loss of product has been provided. Participants found to have a compliance of  $<80\%$  or  $>120\%$  will be counseled.

Protocol 18PEHH: A proof-of-concept study to evaluate the efficacy of Salmon Protein Hydrolysate Powder on energy increase and anti-inflammatory modulation in healthy males and females.

## 7.6 Laboratory Analyses

Blood samples will be drawn from the participants at screening (Visit 1), baseline (visit 2), and the end of Study (Visit 3) as indicated in the schedule of assessments. Blood draws will be performed from a participant's arm via venipuncture. See Section 11.3 for potential risks associated with venipuncture.

Protection of participant confidentiality will extend to all data generated from the assaying of these samples. These samples will be alphanumerically coded and the persons performing the analysis will not be aware of the subject's identity.

At screening (Visit 1), 4 mL of whole blood will be collected in:

1. 1 x 4 mL EDTA vacutainer tube to generate plasma for:
  - a. CBC (1 tube)

At baseline (Visit 2), 23 mL of 8 hour fasting whole blood will be collected in:

1. 1 x 4 mL EDTA vacutainer tube to generate plasma for:
  - a. HbA1c (1 tube)
2. 1 x 4 mL EDTA vacutainer tube for whole blood for:
  - a. Future analysis - Gene expression analysis (1 tube)
3. 3 x 5 mL SST vacutainer tube to generate serum for:
  - a. Future Analysis - ROS/RNS and Inflammatory Cytokines (2 tubes)
  - b. Fasting Glucose (1 tube)

At the end of the study (Visit 3), 27 mL of 8 hour fasting whole blood will be collected in:

1. 2 x 4 mL EDTA vacutainer tube to generate plasma for:
  - a. CBC (1 tube)
  - b. HbA1c (1 tube)
2. 1 x 4 mL EDTA vacutainer tube for whole blood for:
  - a. Future analysis - Gene expression analysis (1 tube)
3. 3 x 5 mL SST vacutainer tube to generate serum for:
  - a. Future Analysis - ROS/RNS and Inflammatory Cytokines (2 tubes)
  - b. Fasting Glucose (1 tube)

The total blood volume collection for the laboratory assessments listed above will be approximately 54 mL, over the period from screening to end of study (approximately 128 days). At any study visit, blood loss per volunteer is not expected to exceed 27 mL. Additional blood samples may be collected during the course of the study in order to perform or repeat laboratory tests outlined in the Schedule of Assessments if needed.

The central laboratory, Life Labs, London Ontario, will be used in this study to measure CBC, HbA1c, and fasting glucose.

Blood collected for future analysis will be shipped to the sponsor.

Urine pregnancy test will be performed at the KGK Science clinic site.

Protocol 18PEHH: A proof-of-concept study to evaluate the efficacy of Salmon Protein Hydrolysate Powder on energy increase and anti-inflammatory modulation in healthy males and females.

### **7.7 Termination of the Trial**

In the case of premature termination of the trial, participating investigators/participants, and the Institutional Review Board must be promptly informed of the termination.

### **7.8 Protocol Amendments**

If amendments to the study protocol are required after approval such changes will be captured in writing the reasons for the change documented and signed and dated by the sponsor. Any such amendments may be subject to IRB and Health Canada review/approval prior to implementation. Exception: if it becomes necessary to alter the protocol to eliminate an immediate hazard to participants, an amendment may be implemented prior to IRB approval. In this circumstance, the Investigator must notify IRB and Health Canada in writing within five (5) working days of the implementation.

Protocol 18PEHH: A proof-of-concept study to evaluate the efficacy of Salmon Protein Hydrolysate Powder on energy increase and anti-inflammatory modulation in healthy males and females.

## 8 SAFETY INSTRUCTIONS AND GUIDANCE

### 8.1 Adverse Events and Laboratory Abnormalities

#### 8.1.1 Adverse Events

An adverse event (AE) is any untoward medical occurrence in a clinical investigation participant who has been administered an investigational product and which does not necessarily have a causal relationship with this treatment. An AE can be any unfavorable and unintended sign (including an abnormal laboratory finding), symptom, or disease temporally associated with the use of a product, whether or not it is considered related to that product. Pre-existing conditions which worsen during a study are to be reported as AEs.

During the study, participants should record any adverse effects in their diary. At each visit the participant will be asked "Have you experienced any difficulties or problems since I saw you last"? Any adverse events (AEs) will be documented and in the study record and will be classified according to the description, duration, intensity, frequency, and outcome. The qualified investigator will assess any AEs and decide causality.

Intensity of AEs will be graded on a three-point scale (mild, moderate, severe) and reported in detail in the study record.

Mild: Awareness of event but easily tolerated

Moderate: Discomfort enough to cause some interference with usual activity

Severe: Inability to carry out usual activity

The causality relationship of investigational product to the adverse event will be assessed by the qualified investigator as either:

Most probable: There is a reasonable relationship between the investigational product and AEs. The event responds to withdrawal of investigational product (dechallenge) and recurs with rechallenge when clinically feasible.

Probable: There is a reasonable relationship between the investigational product and AEs. The event responds to dechallenge.

Possible: There is a reasonable relationship between the investigational product and AEs. Dechallenge information is lacking or unclear.

Unlikely: There is a temporal relationship to the investigational product administration but there is no reasonable causal relationship between the investigational product and the AEs.

Not related: No temporal relationship to the investigational product administration or there is a reasonable causal relationship between non-investigational product, concurrent disease or circumstance and the AEs.

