### **8.3 Reporting of SAEs and Unexpected Adverse Reactions**

The qualified investigator will be responsible for classification of an AE as an SAE within 24 hours of notification. Causality should be signed off by the qualified investigator prior to reporting to ethics and regulatory bodies. Notification of any serious adverse events must be made in writing to the study sponsor. The IRB will be notified of all product related SAEs and unexpected adverse reactions.

KGK Science must notify the TPD of all serious adverse events and reactions as follows:

If it is neither fatal or life threatening, within 15 calendar days after the day on which the sponsor becomes aware of the information; and

If it is fatal or life threatening, must be reported as soon as possible, but not later than seven (7) days after the day on which the sponsor becomes aware of the information.

Protocol 18PEHH:	A proof-of-concept study to evaluate the efficacy of Salmon Protein Hydrolysate Powder on energy increase and anti-inflammatory modulation in healthy males and females.
------------------	--

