#### 9.3.2 Safety

For adverse events, a descriptive analysis will be given. Adverse events will be presented in a frequency table by category and treatment. Furthermore, description, frequency, severity and causality will be reported for each adverse event.

Protocol 18PEHH: A proof-of-concept study to evaluate the efficacy of Salmon Protein Hydrolysate Powder on energy increase and anti-inflammatory modulation in healthy males and females.

Continuous safety parameters (e.g. weight, heart rate and blood pressure) will be summarized using a table including mean, standard deviation, median, minimum value, and maximum value for each measurement point. The changes from baseline will also be summarized similarly.

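### Section 8.1.1 lets an event reasonably related to product be graded 'Not related' when another cause exists, leaves one kind of event ungraded, and is not mapped to the IRB trigger in 8.3

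*Combined protocol and SAP*

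**What the plan says.** Section 8.1.1 leaves the grade to one person: "The qualified investigator will assess any AEs and decide causality". Five grades are offered, with no rule on which prevails if two fit.

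- *Most probable*, *Probable* and *Possible* all start from a reasonable relationship to product and differ by what happened when product was stopped.
  - *Most probable*: "The event responds to withdrawal of investigational product (dechallenge) and recurs with rechallenge when clinically feasible".
  - *Probable*: "The event responds to dechallenge".
  - The third grade reads "Possible: There is a reasonable relationship between the investigational product and AEs. Dechallenge information is lacking or unclear".
- *Unlikely* needs a temporal link but no reasonable causal link to product.
- *Not related* needs either no temporal link, "or there is a reasonable causal relationship between non-investigational product, concurrent disease or circumstance and the AEs".

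Two later sections use the grade. In 9.3.2, "description, frequency, severity and causality will be reported for each adverse event", alongside a frequency table of AEs. In 8.3, "The IRB will be notified of all product related SAEs and unexpected adverse reactions", and "Causality should be signed off by the qualified investigator prior to reporting to ethics and regulatory bodies". Section 8.3 also sends every SAE to the sponsor in writing and every SAE to the regulator, whatever its cause.

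**The concern.** The two ends of the scale are built on different questions. The three related grades ask whether product is a reasonable cause. The second limb of *Not related* asks only whether something else is. Both answers can be yes for the same event, and the text then supports opposite grades. Separately, the three related grades cover a positive dechallenge and a missing or unclear one, but not a clearly negative one.

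This is an open-label study with one arm of 20 (Section 4), and AE incidence is a safety outcome (Section 3). With no control group, the investigator's grade is the only attribution of AEs to product that the study will produce. The same assessment bears on which SAEs go to the IRB, because 8.3 limits that notice to product-related SAEs and unexpected adverse reactions and does not say which grades count as product-related.

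**Working it through.** The plan states no figure on this point, so there is nothing numeric to reproduce. The check sets each possible kind of event against the definitions as written.

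**Inputs, all from 8.1.1.** For an event with a temporal link to product, three facts decide the grade:
- product is a reasonable cause: yes or no (2);
- dechallenge: positive with recurrence on rechallenge, positive only, negative, or lacking/unclear (4);
- another reasonable cause exists: yes or no (2).

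Profiles: 2 × 4 × 2 = 16.

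**Grades met as written**

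| Product a reasonable cause? | Dechallenge | No other cause | Another reasonable cause |
|---|---|---|---|
| Yes | Positive, recurs | Most probable, Probable | Most probable, Probable, **Not related** |
| Yes | Positive | Probable | Probable, **Not related** |
| Yes | Negative | **none** | **Not related** only |
| Yes | Lacking/unclear | Possible | Possible, **Not related** |
| No | Any of the 4 | Unlikely | Unlikely, Not related |

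**Counts**
- More than one grade: 1 + 3 + 4 = 8. The 1 is *Most probable* nested in *Probable*, which is an ordinary ordered overlap and harmless. The 3 meet a related grade and *Not related* together. The 4 meet *Unlikely* and *Not related* together.
- Exactly one grade: 7. One of these is a profile in which product is a reasonable cause, yet the only grade met is *Not related*.
- No grade: 1.
- Total: 8 + 7 + 1 = 16.

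Of the 8 profiles in which product is a reasonable cause, 3 + 1 + 1 = 5 are therefore contradictory, wrongly placed or unplaced. These are counts of logical profiles, not event frequencies.

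**Can the ungraded profile arise?** Yes, under the protocol's own rules. Section 8.2.2 takes a participant with clinically significant, unexplained laboratory abnormalities off product and keeps them attending visits. That can yield dechallenge information in a case with no identified alternative cause. Section 8.2.1 also foresees AEs for which neither return to baseline nor stabilization can be established.

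**Link to 8.3.** An SAE with two reasonable causes can be graded *Not related* in full accord with 8.1.1. It then need not count as product-related. The other IRB category, unexpected adverse reactions, does not reliably bring it back: 8.1.3 defines *unexpected* but ties *reaction* to none of the five grades.

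**Effect of rewording**
- Changing only the second limb of *Not related*, so that it also requires no reasonable relationship to product, takes the conflicts with related grades from 3 to 0. It raises the ungraded profiles from 1 to 2, because the negative-dechallenge profile with another cause loses its only grade. The gap needs its own wording.
- Under the full rewording given in the fix, 14 profiles meet exactly one grade, 2 meet *Most probable* and *Probable* (the harmless nesting), and none is ungraded: 14 + 2 + 0 = 16.

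**The case against.** The best defence is that 8.1.1 asks for a single considered grade. An experienced investigator facing two reasonable causes would often record *Possible*, and might call a failure to resolve unclear. Section 9.3.2 lists every AE with its description and plans no total of related AEs, so in 20 participants a reader can see each event. Section 11.1 binds the site to all IRB requirements, which may include wider local safety reporting.

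Much of this stands, and it limits the point. It does not remove it, because the text equally permits *Not related*, and for one profile permits nothing else.

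A reader might infer more than the documents support:

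- *That related SAEs go unreported.* Only the IRB route is exposed, and only if the grade chosen is *Not related*. The sponsor and regulator receive all SAEs.
- *That the number of related events could be anything from all to none.* That holds only for events with another reasonable cause and a dechallenge that is positive, lacking or unclear. With no other cause and a dechallenge that is not negative, only related grades fit. With a negative dechallenge, no related grade is available.
- *That nearly every common complaint could be graded Not related.* The documents do not say how often AEs have another cause, and the test is a reasonable causal relationship, which is narrower than a merely plausible alternative.
- *That all persistent harms are ungraded.* If product was never stopped, dechallenge information is lacking and *Possible* applies. If another cause exists, *Not related* applies.
- *That causality sign-off can hold back regulator reports.* Section 8.3 says sign-off should come first, but its limits of 15 calendar days, or 7 days for fatal or life-threatening events, are mandatory, and nothing suspends them.

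**Conclusion.** The concern holds as a defect in stated definitions, not as missing detail. Read as written, 8.1.1 can place an event with a reasonable relationship to product under *Not related*, and gives no grade to a reasonably related event with a negative dechallenge and no other cause. The consequences are a possible distortion of the related/not-related split reported under 9.3.2, and an SAE with two reasonable causes that may fall outside the IRB trigger in 8.3.

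The size is bounded. Total AE counts do not change, and neither does SAE reporting to the sponsor or regulator. The documents give no AE or SAE rate, so the number of events affected cannot be estimated and may be zero in 20 participants. The conclusion rests on reading the definitions literally and on the absence of any precedence rule. Whether an event is misclassified depends on the grade the investigator picks, except with a negative dechallenge, where the text offers either *Not related* or nothing.

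**What to change.** Reword 8.1.1:

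- *Not related*: no temporal relationship, or another cause explains the event **and** there is no reasonable relationship to product.
- *Unlikely*: temporal relationship, no reasonable relationship to product, and no other cause identified.
- *Possible*: reasonable relationship to product, with dechallenge lacking, unclear **or negative**.
- Add a sentence that another reasonable cause does not by itself move an event out of *Possible*, *Probable* or *Most probable*.

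In 8.3, define product-related as *Possible* or higher, so that the IRB trigger follows from the grade.

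A general instruction to record the more related of two grades is not a substitute. Any temporally linked event with no reasonable relationship to product would meet *Unlikely* as now worded, so the second limb of *Not related* could never be used.

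The cost is a few lines of protocol text and matching CRF guidance, with no change to treatment, visits or sample size. The one downside is that somewhat more events may be graded *Possible*.
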